*A mean of 2 semen samples at Screening must meet the following minimum criteria: semen volume ≥ 1.5 mL, total sperm/ejaculate ≥ 39 million, sperm concentration ≥ 15 million/mL, sperm total motility $\geq 40\%$, and normal sperm morphology $\geq 30\%$
†All subjects with $\geq 50\%$ decrease in sperm concentration and/or sperm motility and/or sperm morphology as compared to baseline will enter a Monitoring Phase (discontinue study drug and evaluate for Reversibility)
‡ At After Week 13, protocol design allows a switch to open-label filgotinib for Non-responders or those with Disease Worsening; semen analysis is required to confirm that no pre-specified decrease threshold is met, prior to administration of open-label filgotinib

There are 5 distinct parts to the study which subjects may enter depending upon the individual subject's response of the underlying IBD to assigned treatment and/or observed changes in semen parameters. The 5 parts which are described in the following sections comprise of the following:

- 1) Part A (Day 1 through Week 13 Study Visit)
- 2) Part B (After Week 13 through Week 26 Study Visit)
- 3) Open-Label Filgotinib Phase
- 4) Monitoring Phase
- 5) Long Term Extension

The study parts are described in the following sections.

Part A (Day 1 through Week 13 Study Visit)

(Appendix 11 and Figure 3-2)

In Part A, all subjects will receive blinded study drug for the first 13 weeks, starting from the Day 1/Randomization Study Visit. At the Week 13 Study Visit, IBD response status (ie, Non-responder vs Responder, see Definition of Terms) will be determined based on the partial Mayo Clinic Score (partial MCS) for subjects with UC, or the Crohn's Disease Activity Index (CDAI) for subjects with CD. In addition, sperm parameters (see Section 6.13 Semen Collection Procedure) will be evaluated to determine whether any of the pre-specified decrease thresholds (see Definition of Terms) have been met.

- Subjects who are Responders and whose sperm parameters do not meet a pre-specified decrease threshold will continue blinded study drug in Part B.
- Subjects who are Non-responders and whose sperm parameters do not meet a pre-specified decrease threshold will discontinue blinded study drug and commence open-label (OL) filgotinib.
- Subjects whose sperm parameters meet a pre-specified decrease threshold, regardless of IBD response status, will discontinue blinded study drug and enter the Monitoring Phase.

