- 5) Long Term Extension

The study parts are described in the following sections.

Subjects will visit the clinical study center to be evaluated for clinical and laboratory assessments at Screening, Day 1, Week 2, Week 4, Week 8, and Week 13, including semen sample collection during Week 13 visits. Subjects who continue on blinded treatment after the first 13 weeks of treatment will return for Week 20 and Week 26 assessments, including semen sample collection during Week 26 visits.

[figure not shown]
Figure 3-2. Part A (Day 1 through Week 13 Study Visit)

In Part A, all subjects will receive blinded study drug for the first 13 weeks, starting from the Day 1/Randomization Study Visit. At the Week 13 Study Visit, IBD response status (ie, Non-responder vs Responder, see Definition of Terms) will be determined based on the partial Mayo Clinic Score (partial MCS) for subjects with UC, or Crohn’s Disease Activity Index (CDAI) for subjects with CD. In addition, sperm parameters (see Section 6.13 Semen Collection Procedure) will be evaluated to determine whether any of the pre-specified decrease thresholds (see Definition of Terms) have been met.

- Subjects who are Responders whose sperm parameters do not meet a pre-specified decrease threshold will continue blinded study drug in Part B.
- Subjects who are Non-responders whose sperm parameters do not meet a pre-specified decrease threshold will discontinue blinded study drug and commence open-label (OL) filgotinib.
- Subjects whose sperm parameters meet a pre-specified decrease threshold, regardless of IBD response status, will discontinue blinded study drug and enter the Monitoring Phase.

[figure not shown]
Figure 3-3. Part B (After Week 13 through Week 26 Study Visit)

In Part B, all subjects will continue on blinded study drug for up to an additional 13 weeks. Subjects may experience Disease Worsening (see Definition of Terms) of their underlying IBD at any time during blinded study drug treatment (after Week 13 through Week 26). If Disease Worsening is confirmed, sperm parameters will be evaluated to determine whether a pre-specified decrease threshold has been met prior to a study drug change (changing from blinded study drug to OL filgotinib). Based upon the sperm parameters at this time point, subjects may follow one of the following pathways:

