3.4. Disease Worsening Criteria

Subjects meeting the following Disease Worsening criteria, evaluated after Week 13 through Week 26, must be discontinued from blinded treatment. These subjects will be offered the option to commence OL filgotinib 200 mg once daily, as long as they have not experienced a decrease of $\geq 50\%$ from baseline in sperm concentration, and/or motility, and/or morphology.

Upon confirmation of Disease Worsening and before switching to the OL Filgotinib Phase, 2 semen samples will be collected. Disease Worsening is confirmed at the time of the second consecutive visit. If the second Disease Worsening visit occurs during the 14-day semen

collection window for the Week 13 or Week 26 Study Visit, the routine Week 13 or Week 26 semen collection will suffice.

Disease Worsening assessments will be driven by the patient history, physical and laboratory examinations and are based on the following criteria:

For subjects with UC, Disease Worsening is defined by a partial MCS after Week 13 consisting of:

- An increase of ≥ 3 points to at least 5 points from the Week 13 value on 2 consecutive visits, OR
- An increase to 9 points from the Week 13 value on 2 consecutive visits, if the Week 13 value was > 6 points

For subjects with CD, Disease Worsening is defined by a total CDAI score after Week 13 consisting of:

- A score ≥ 220 on 2 consecutive visits, AND
- An increase of ≥ 100 points from the Week 13 value on 2 consecutive visits

For all subjects, Disease Worsening is further defined by:

- Disease Worsening to the extent that the subject requires medications prohibited by the study (at investigator's discretion, with discussion with the medical monitor or designee if feasible); these subjects do not qualify to receive OL filgotinib 200 mg once daily.

Disease Worsening visits may include Unscheduled Visits (eg, a Study Visit followed by an Unscheduled Visit, or 2 sequential Unscheduled Visits after Week 13).

In the LTE, subjects who meet Disease Worsening criteria (per above criteria), or have Disease Worsening per investigator judgment, should be discontinued from study drug. These subjects should complete an ET visit (which includes semen collection), followed by a routine safety follow-up visit 30 days after the last dose of study drug.

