- n Chest x-ray (views as per local guidelines) taken at Screening or within the 3 months prior to Screening (with the report or films available for investigator review) without evidence of active or latent TB infection
- o As detailed in Appendix 6. For visits that require fasting, subjects should not have any food or drink (except water) for at least 8 hours before the visit.
- p Lipid profile should be performed every 26 weeks
- q Semen samples will be collected on the visit day and/or after the visit. Those meeting the pre-specified decrease threshold in sperm parameters (as defined in the Definition of Terms) must enter the Monitoring Phase (see schedule below).
- r The screening semen sample collection should coincide with the Day 1 (baseline) visit as much as possible.
- s At time of confirmation of Non-responder status/Disease Worsening and prior to initiation of open-label filgotinib, Semen Analysis must confirm subject did not meet the pre-specified decrease threshold in sperm parameters.
- t At time of confirmation of Non-responder status/Disease Worsening and prior to entry into the LTE, Semen Analysis must confirm subject did not meet the pre-specified decrease threshold in sperm parameters.
- u This question will be asked prior to each semen collection.
- v An HIV-1/HIV-2 antigen/antibody test, a Hepatitis C virus antibody test, a Hepatitis B surface antigen, a Hepatitis B surface antibody and a Hepatitis core antibody test will be conducted on all subjects; Subjects with positive Hepatitis B surface antigen (HBsAg) at Screening are excluded from the study. Subjects with positive HBV core Ab and negative HBsAg, require reflex testing for HBV DNA. Subjects with positive HBV DNA at Screening will be excluded. Subjects with positive HBV core Ab and negative HBV DNA are eligible per investigator judgment, but may require prophylactic treatment in accordance with HBV treatment guidelines/local standard of care and require ongoing monitoring with blood tests for HBV DNA every 3 months. Subjects with evidence of active Hepatitis B during the study, as evidenced by HBV DNA positivity, will be discontinued from study drug as outlined in the protocol. Subjects with positive HCV antibody (Ab) at Screening, require reflex testing for HCV RNA. Subjects with positive HCV RNA at Screening will be excluded. Subjects with positive HCV Ab, but negative HCV RNA are eligible per investigator judgment.

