Week 221	1548	1535	≥ 1548
FU-4*	Last Dose Date any study drug + 30 days	Last Dose Date any study drug + 8 days	Last Dose Date any study drug + 35 days

Note: Primary analysis includes data up to first dose date of open-label filgotinib (if non-missing) or to last dose date of double-blind drug + 7 days (for those who do not switch to open-label filgotinib).

Secondary analysis includes all “on-treatment” data up to the last dose date of any study drug + 7 days.

*FU-4 visit for subjects who have stopped all study drugs and had a 30-day safety FU visit ± 5 days will be displayed in listings only.

Table 3-4. Analysis Visit Windows for On-Treatment Semen Parameters

Analysis Visit	Nominal Day (Study Day)	Lower Limit (Study Day)	Upper Limit (Study Day)
Baseline	1	None	1
Week 13	92	85	112
Week 26	183	170	260
Week 39	274	261	351
Week 52	365	352	442
Week 65	456	443	533
Week 78	547	534	624
Week 91	638	625	715
Week 104	729	716	806
Week 117	820	807	897
Week 130	911	898	988
Week 143	1002	989	1079
Week 156	1093	1080	1170
Week 169	1184	1171	1261
Week 182	1275	1262	1352
Week 195	1366	1353	1443
Week 208	1457	1444	1534
Week 221	1548	1535	≥ 1548

Note: Primary analysis includes data up to first dose date of open-label filgotinib (if non-missing) or to last dose date of double-blind drug + 7 days (for those who do not switch to open-label filgotinib).

Secondary analysis includes all “on-treatment” data up to the last dose date of any study drug + 7 days.

Table 3-5. Analysis Visit Windows for Semen Parameters in Monitoring Phase (Calculated from Last Dose Date of Any Study Drug)

Analysis Visit	Nominal Day (FU Day)	Lower Limit (FU Day)	Upper Limit (FU Day)
MP Week 13	91	8	104
MP Week 26	182	105	195
MP Week 39	273	196	286
MP Week 52	364	287	377

MP = Monitoring Phase; FU = Follow-Up.

NOTE: All visit windows for monitoring phase will be calculated from last dose date of any study drug.

FU Day = visit date – last dose date of any study drug.

Investigator Assessment of ECG Visit Assignment

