6.2. Primary Analysis of Primary and Secondary Endpoints

The primary analysis will be an observed cases analysis at Week 13 while subjects are on double-blind study drug as described in FDA’s guidance for industry on testicular toxicity studies {U. S. Department of Health and Human Services (DHHS) 2018}.

The main estimators of a While on Treatment Strategy estimand will be utilized for the primary analysis of primary and secondary endpoints at Week 13:

BINARY ENDPOINT	WHILE ON-TREATMENT STRATEGY
Population	Semen Analysis Set (subjects with 2 evaluable semen samples collected at baseline and at the Week 13 analysis visit) as defined in Section 3.1.2 of this SAP.
Patient Level Outcome to be Measured	Binary outcome for a subject meeting a $\geq 50\%$ decrease from baseline in sperm concentration at Week 13. Outcome is determined based on the mean of 2 evaluable semen samples at a visit.
Measure of intervention effect and handling of intercurrent events	Measure of treatment effect assuming that the treatment effect prior to the intercurrent event of treatment early termination is of interest. Data included to last dose date double-blind drug + 7 days will be considered “while on-treatment” for those who permanently discontinue double-blind study drug.
Population level summary measure	Difference in a binary outcome, comparing those assigned to filgotinib versus those assigned to placebo.
Estimators	
Main estimator: A stratified Mantel-Haenszel test (stratification factor: sperm concentration [15 - 50 and > 50 M/mL]) will be used to estimate the difference in proportions (filgotinib – placebo) and corresponding 95% CI {Koch 1989}. Calculations are provided in Appendix 2.
 
Note: When performing the stratified Mantel-Haenszel test, the 15 - 25 and > 25 - 50 M/mL strata for sperm concentration will be combined (eg, 15 - 50 M/mL) due to the small number of subjects in the lowest stratum; disease type will not be included as a stratification factor due to the small number of subjects with CD; and no subjects in this study received MTX.

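### For subjects who stop blinded drug for Non-response or Disease Worsening, the SAP table notes let the semen result decide whether a late semen pair is analysed, and SAP 6.2 states a different cut-off

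*SAP*

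**What the plan says.** SAP 3.7.2, note to Table 3-4 (semen), repeated under Table 3-3 (hormones): "Primary analysis includes data up to first dose date of open-label filgotinib (if non-missing") for switchers, "or to last dose date of double-blind drug + 7 days (for those who do not switch to open-label filgotinib") for the rest. The first branch has no limit on days since the last blinded dose.

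SAP 6.2, the estimand for the primary analysis, counts data to last double-blind dose + 7 days as on treatment "for those who permanently discontinue double-blind study drug". It makes no exception for switchers, and Protocol 3.3.2 describes switchers as having permanently stopped blinded drug.

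Protocol Section 3 sets the Week 13 pathways. "Subjects who are Non-responders whose sperm parameters do not meet a pre-specified decrease threshold will discontinue blinded study drug and commence open-label" filgotinib; by contrast, "Subjects whose sperm parameters meet a pre-specified decrease threshold, regardless of IBD response status, will discontinue blinded study drug and enter the Monitoring Phase". For Part B, Protocol 3.4 says: "Upon confirmation of Disease Worsening and before switching to the OL Filgotinib Phase, 2 semen samples will be collected". Protocol 6.6 requires both samples to be analysed before the switch. Appendix 2, footnote q, allows sampling on or after the visit day: "Semen samples will be collected on the visit day and/or after the visit".

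**The concern.** In one branch of the trial the cut-off depends on the outcome. Take two Week 13 Non-responders with identical dosing and sampling dates, both first sampled 10 days after the last blinded dose and inside the Week 13 window. The one without a decrease starts OL filgotinib and his pair counts. The one with a decrease enters the Monitoring Phase and his pair is cut at + 7 days. The event leaves the analysis while the matching non-event stays in the denominator.

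Any single limit, long or short, would treat the two alike. The trouble is a limit that binds on only one result. In a study designed to detect testicular harm, the loss runs towards fewer decreases and, if filgotinib causes more of them, towards a smaller difference. Separately, two programmers working from SAP 3.7.2 and SAP 6.2 could build different primary datasets.

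**Working it through.** **The plan's own figure.** Protocol 8.7: 100 evaluable per group with 20% non-evaluable gives 100/(1 − 0.20) = 125 per arm, 250 in total. This reproduces. The plan states no event rate, margin or count of late pairs, so the sizes in steps 4 and 5 rest on assumed inputs.

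**1. Which limit applies on each pathway** (Protocol 3, 3.4; SAP 3.7.2, 6.2)

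| Subject | Semen result | Next step | Limit under the notes | Limit under 6.2 |
|---|---|---|---|---|
| Week 13 Responder | no decrease | stays on blinded drug | not binding; last dose comes later | not binding |
| Week 13 Non-responder | no decrease | OL filgotinib | first OL dose | + 7 days |
| Week 13 Non-responder | decrease | Monitoring Phase | + 7 days | + 7 days |
| Part B Disease Worsening, OL-eligible | no decrease | OL filgotinib | first OL dose | + 7 days |
| Part B Disease Worsening | decrease | Monitoring Phase | + 7 days | + 7 days |
| Week 26 Non-responder, no worsening | no decrease | stops, no OL | + 7 days | + 7 days |
| Stops for another reason, no OL | either | no OL | + 7 days | + 7 days |

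Only rows 2 and 3, and rows 4 and 5, are treated differently according to the result, and only under the notes.

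**2. Days exposed at Week 13.** The window is Days 85 to 112 (Table 3-4), and a pair is dated by its earliest valid sample (SAP 3.7.3). With last blinded dose on Day L, a non-switcher's upper limit is min(112, L + 7).

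- L = 92: limit Day 99, so Days 100–112 (13 of 28 days) are open only to switchers.
- L = 97: limit Day 104, so Days 105–112 (8 days).
- L = 105 or later: none.

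A dropped pair falls in the first Monitoring Phase window, which opens at follow-up Day 8 (Table 3-5).

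**3. Direction.** Let N pairs include E with a threshold decrease. Among the late pairs, e show a decrease and m do not.

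- Keep all late pairs: E/N.
- Drop all late pairs: (E − e)/(N − e − m).
- The notes: (E − e)/(N − e).

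The third is never larger than either of the others. This is exact for threshold decreases of any kind. For sperm concentration alone it holds for pairs that qualified on concentration. A pair qualifying only on motility or morphology leaves as a non-event, which the formula below ignores.

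**4. Size at Week 13, assumed inputs.** With E = pN and e = fE, the observed rate is p(1 − f)/(1 − pf).

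| f (assumed) | p = 10% reads | p = 20% reads | True 10.0-point difference reads |
|---|---|---|---|
| 0 | 10.0% | 20.0% | 10.0 |
| 2% | 9.8% | 19.7% | 9.9 |
| 5% | 9.5% | 19.2% | 9.6 |
| 10% | 9.1% | 18.4% | 9.3 |
| 20% | 8.2% | 16.7% | 8.5 |

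Example: p = 0.20, f = 0.20 gives 0.16/0.96 = 0.167; p = 0.10 gives 0.08/0.98 = 0.082.

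**5. Effect on the planned interval, assumed counts.** SAP Appendix 2 formula, 100 per arm, two strata of 50, 16 filgotinib versus 8 placebo events:

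- All pairs kept: 8.0 points (95% CI −1.3 to 17.3).
- One late filgotinib event dropped: 7.1 (−2.0 to 16.3).
- Two dropped, one per stratum (7/49 versus 4/50 in each): 6.3 (−2.8 to 15.4).

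These cases drop filgotinib events only. Losses in both arms would offset in part.

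**The case against.** The strongest reply is that the planned sequence leaves few late pairs. A subject with a decrease usually stops because of the semen result, so the sample comes first. Drug is taken in clinic and dispensed at Week 13 (Protocol Appendix 2), and SAP 1.2 says switching or stopping may not happen until after that visit because samples take time to collect and read. For Disease Worsening, Protocol 3.4 requires sampling before the switch to OL but does not say that blinded drug is stopped before sampling. This stands: f is probably small at Week 13, and nothing in the documents supports a particular value. It does not show that f is zero, since sampling may follow the visit and an invalid first sample moves the pair's date later.

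Second, if SAP 6.2 governs, switchers are cut at + 7 days too and the asymmetry disappears. That also stands, but the SAP does not say which passage prevails, and the table notes name the primary analysis expressly.

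Third, the events would not vanish from the report. SAP 6.2 adds a count of concentration decreases at any time up to Week 26, SAP 4.1 tabulates entries to the Monitoring Phase by arm, and SAP 6.6.2 lists semen data for those subjects. This is true, but none of it restores a dropped pair to the primary proportion, and the SAP does not say whether the any-time count follows the + 7 limit.

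**Conclusion.** The point holds for one subgroup: subjects who stop blinded drug for Week 13 Non-response or Part B Disease Worsening and are otherwise eligible for OL filgotinib. There, the notes make inclusion of a late pair depend on its result, and they conflict with SAP 6.2. The direction is certain for threshold decreases; the size is unknown, probably small at Week 13, and zero if there are no late pairs.

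A reader might infer more, and the documents do not support it:

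- *That any late pair is kept or dropped by its result.* Subjects who stop for other reasons without starting OL, and Week 26 Non-responders, are cut at + 7 days whatever the result. IBD response also helps decide the pathway.
- *That the Week 26 visit is affected in general.* Without Disease Worsening it has no OL pathway. Only Disease Worsening pairs first sampled within Days 170–260 can enter the Week 26 proportion.
- *That off-drug values of any age count for switchers.* The visit windows close at Day 112 and Day 260.
- *That each arm's rate is shown to be biased.* That needs late pairs with a decrease and the notes prevailing over 6.2.

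Two assumptions remain. The + 7 limit is taken to be tested on the first evaluable sample, as for visit windows, though the SAP does not say so. SAP 3.1.2 was not in the text I read, so any cut-off stated there is unchecked.

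**What to change.** Replace the notes to Tables 3-3 and 3-4 with one rule for every subject, consistent with SAP 6.2: double-blind analyses include data up to the earlier of (a) the first OL filgotinib dose and (b) the last double-blind dose + 7 days, whatever pathway follows, with a semen pair judged by the date of its first evaluable sample. State whether the count of decreases at any time up to Week 26 follows the same limit. List by arm the pairs that the rule excludes, with their results, so that a reader can see whether anything turned on it.

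The cost is a sentence in the SAP, one derivation and one listing. The downside is that a few switchers' late pairs without a decrease leave the double-blind analysis. SAP Section 1 sends changes made after finalisation to the clinical study report, so the change would be recorded there.

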- w Subjects with positive HBV core Ab and negative HBV DNA at Screening require ongoing monitoring with blood tests for HBV DNA every 3 months
- x Sparse plasma PK samples are collected at least 30 minutes post-dose.
- y Sparse plasma PK samples can be collected at any time without regard to dosing.
- z Sparse plasma PK samples are collected pre-dose.
- aa The subject will take the first dose (Day 1) in the clinical study center. For PK collection purposes, at Weeks 2, 13, and 26, and OL Weeks 2 and 13, subjects should be instructed not to take their study drug, but rather to bring it with them to the clinic. Subjects will be instructed to take their dose during their scheduled visit, as detailed in Section 6.16.

Study Procedure	Monitoring Phase (Section 6.7)	ET ^a
	Visits occur every 13 weeks (±5 days) for up to 52 weeks or until Reversibility is met, whichever is sooner	
Symptom-directed Physical Exam, as needed	X	X
Vital Signs ^b and Weight	X	X
12-lead ECG		X
Partial Mayo Clinic Score (partial MCS) ^c		X
Crohn's Disease Activity Index (CDAI) ^d		X
Urinalysis ^e	X	X
Hematology and Chemistry ^e	X	X
LH, FSH, inhibin B, total Testosterone ^e collection time between 07:00-11:00 in the morning	X	X
Concomitant Medications	X	X
Assessment of Adverse Events ^f	X	X
Semen Collection (2 samples as per collection instructions in Section 6.13) ^g	X	
Date and time of most recent ejaculation ^h	X	

a Not required if Reversibility is met or if subject completes Week 52

b As detailed in [Appendix 7](#)

c Partial MCS includes all parts of the complete MCS except endoscopy. For definitions of IBD response status, please refer to Definition of Terms; for definitions of Disease Worsening, please refer to Section 3.4 and Definition of Terms. Subject recall for the last 24 hours will be used for the patient reported components of the complete MCS and partial MCS. MCS and partial MCS will be collected for UC patients. Physician Global Assessment is a component of MCS and partial MCS.

d CDAI will be collected for CD patients. Subject recall for the last 7 days will be used for the patient reported outcomes of the CDAI. The CDAI score calculations should not be inclusive of days that involve an endoscopy procedure or preparation for that procedure.

e As detailed in [Appendix 6](#)

f As detailed in Section 7.3

g Semen samples will be collected on the visit day and/or after the visit

h This question will be asked prior to each semen collection

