Prior to Protocol Amendment 2, subjects who switched to OL filgotinib and subjects who discontinued study drug after meeting pre-specified sperm decrease threshold(s) continued to attend visits scheduled relative to the date of their first dose of double-blind study drug (eg, the Week 26 visit was scheduled approximately 26 weeks after the first dose of double-blind study drug). However, because of the time required to collect and evaluate semen samples, subjects may not have switched or discontinued, respectively, until after the Week 13 visit. Therefore, a full 13 weeks (ie, a full spermatogenic cycle) may not have passed before their next scheduled semen assessment under the new condition (ie, since switching to OL filgotinib or discontinuing study drug, respectively). At/after Protocol Amendment 2, study visits in the OL Filgotinib Phase and Monitoring Phase are scheduled relative to the first day of starting OL filgotinib and the last day of study drug, respectively, allowing a full 13 weeks before the first semen assessment under the new condition.

Please refer to the study protocol for detailed descriptions of the visit schedule and respective evaluations.

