6.5. Other Displays of Sperm/Semen Data

6.5.1. Treatment-Sequence Semen Displays (Week 26/OL Week 13 and Extension Phase)

The proportion of subjects with a $\geq 50\%$ decrease from baseline in sperm concentration will be presented by treatment sequence and analysis visit. An exact 95% CI for the proportion of subjects with a $\geq 50\%$ decrease from baseline in sperm concentration at Week 26/OL Week 13 within treatment sequence will be presented based on the Clopper-Pearson method.

Descriptive statistics will be presented at Baseline, Week 26/OL Week 13 and subsequent visits by actual treatment sequence to explore the confounding effects of IBD response to treatment. A 95% distribution-free CI on the median change and percentage change from baseline in sperm/semen parameters at Week 26/OL Week 13 will be constructed by treatment sequence using the CIPCTLDF option in PROC UNIVARIATE in SAS. Study days will be used for assignment of analysis visit windows for subjects who stayed on randomized drug throughout study and for subjects who started on double-blind filgotinib and switched to open-label filgotinib. For subjects who switched from placebo to open-label filgotinib, days on open-label filgotinib will be used to assign analysis visit windows. Week 26 for the first 3 treatment

sequences will be displayed along-side OL Week 13 for placebo to OL filgotinib group; Week 39 alongside OL Week 26 for placebo to OL filgotinib group, etc. to align with the originally planned study weeks, but using the at/after Protocol Amendment 3 visit schedule to ensure that subjects who switched from placebo to open-label filgotinib had at least 85 days on filgotinib prior to their first semen collection while on filgotinib treatment (eg, a full sperm cycle).

A cumulative distribution plot for percentage change from baseline in sperm concentration at the Week 26/OL Week 13 visit will be constructed by treatment sequence for subjects who are still on study drug at Week 26/OL Week 13.

The number of days on filgotinib at the time of the first of 2 semen assessments at the Week 26/Open-Label Week 13 analysis visit will be summarized by treatment sequence for subjects with evaluable samples in the analysis visit window.

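### SAP Table 3-5: Monitoring Phase semen windows close 13 days after nominal and none exists after FU Day 377, so an occasional late but compliant collection is labelled one visit late or, at Week 52, gets no visit

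*SAP*

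**What the plan says.** SAP Table 3-5 gives nominal day, lower limit and upper limit, in FU days:

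- "MP Week 13 91 8 104"
- "MP Week 26 182 105 195"
- "MP Week 39 273 196 286"
- "MP Week 52 364 287 377"

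The table note adds: "All visit windows for monitoring phase will be calculated from last dose date of any study drug". No row follows MP Week 52. In SAP Table 3-4 (on-treatment semen), the last row has an open upper limit.

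Five other rules decide where a collection lands:

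- **Visit tolerance.** Protocol Appendix 2 schedules Monitoring Phase visits every 13 weeks, ±5 days.
- **Collection after the visit.** A footnote there says: "Semen samples will be collected on the visit day and/or after the visit".
- **Two samples.** Protocol 6.13 asks for two samples within 14 days, each after at least 48 hours without ejaculation. An approved third sample must come within 14 days of the one before it.
- **Dating.** SAP 3.7.3 assigns the pair to a window by its earliest valid sample. If several collections fall in one window, the one closest to nominal is used.
- **Reporting.** SAP 6.6.2 reports reversibility by visit and cumulatively, with a by-subject listing that flags the reversing measurement. SAP 4.1 takes Monitoring Phase completion from the Study Completion eCRF.

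**The concern.** Relative to a scheduled visit, collection can only lag. Yet Table 3-5 puts its long tail on the early side: −77/+13 days at MP Week 26, the reverse of −13/+77 at Week 26 in Table 3-4. A collection on FU Day 105 is 14 days from nominal Week 13 and 77 days from nominal Week 26, but it is labelled MP Week 26.

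Two things are at stake. A recovery at a late MP Week 13, 26 or 39 collection is tabulated one visit later than it was seen. A recovery at a late MP Week 52 collection, the last chance to show one, has no cell in the table at all. Reversibility is exploratory, but SAP 2.4 builds an analysis around it at the request of the US regulator.

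**Working it through.** **1. Reproduce Table 3-5.** Nominal = 91 × k for k = 1 to 4. Upper limit = nominal + 13. Lower limit = previous upper limit + 1. The first lower limit is the day after the on-treatment cut-off of last dose + 7 days, so 7 + 1 = 8. This gives 8–104, 105–195, 196–286 and 287–377, which matches all four rows. The windows open 91 − 8 = 83 days early at Week 13 and 77 days early at the other visits (for example 182 − 105).

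**2. Valid first sample on the visit day.** The pair is dated nominal −5 to +5: FU Days 86–96 at Week 13 and 359–369 at Week 52. All fall inside, with 104 − 96 = 377 − 369 = 8 days to spare, however late the second sample is.

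**3. First sample after the visit, both samples within 14 days of the visit.** The second sample is at least 2 days after the first, so the latest first sample is visit + 12. With the visit at +5, that is nominal + 17.

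**4. First sample invalid and replaced.** The pair is dated by the second sample, at latest visit + 14. With the visit at +5, that is nominal + 19.

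| Visit | Nominal | Upper limit | Latest, step 3 | Latest, step 4 | Lands in |
|---|---|---|---|---|---|
| MP Week 13 | 91 | 104 | 108 | 110 | MP Week 26 |
| MP Week 26 | 182 | 195 | 199 | 201 | MP Week 39 |
| MP Week 39 | 273 | 286 | 290 | 292 | MP Week 52 |
| MP Week 52 | 364 | 377 | 381 | 383 | no window |

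Reading the 14-day period as a 13-day gap lowers each of these maxima by one day.

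**5. How narrow the overshoot is.** In step 3 there are 11 visit offsets × 91 allowed sample pairs = 1001 date combinations. A pair falls outside only if the visit is 2–5 days late and the first sample comes 9–12 days after it. The count is 1 + 3 + 6 + 10 = 20 (visit at +2, +3, +4, +5). With an invalid visit-day sample, the count is 1 + 2 + 3 + 4 + 5 + 6 = 21 of 143. These are counts of combinations, not probabilities.

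**6. Early side.** On the current schedule nothing is due before 91 − 5 = FU Day 86. For subjects on the pre-Amendment 2 schedule, SAP 1.2 says that "a full 13 weeks (ie, a full spermatogenic cycle) may not have passed before their next scheduled semen assessment under the new condition". If drug stopped 14, 28 or 56 days after the Week 13 nominal day (assumed lags), the first off-drug collection falls on Day 91 − lag = 77, 63 or 35. All are labelled MP Week 13.

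**7. Anchor.** One paragraph of SAP 1.2 counts the 13-week intervals from entry into the Monitoring Phase. Protocol 6.7 counts from drug discontinuation, and Table 3-5 from last dose. If visits ran from an entry 14 days after last dose, nominal visits would fall on Days 105, 196, 287 and 378. Each would move one window on, and Week 52 would be lost. At 13 days they would just fit (104, 195, 286, 377).

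**The case against.** The best defence is that this is a corner case. Routine collections fit, and the breach in step 3 is at most 4 days (6 in step 4). The note to Table 3-5 computes FU Day from the visit date. Read literally, that would keep every compliant visit within nominal +5. The early tail also has a purpose: it keeps successive 13-week collections of pre-Amendment 2 subjects in successive windows for stop lags up to 77 days (182 − 77 = 105). A reversal after Day 377 would still appear in the flagged listing and in eCRF-based disposition. The endpoint is exploratory, with no test or confidence interval.

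Most of this stands, and it limits the point to a tidy-up. Three things remain. SAP 3.7.1 uses the assessment date and SAP 3.7.3 the earliest valid sample, so the visit-date reading is not settled. The protocol does not say that the 14 days start at the visit, so a later first sample cannot be excluded. SAP 3.7.2 has windows because visits may miss their planned days, and a Week 52 collection 14 or more days late has none.

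A reader might infer that samples soon after stopping produce false Week 13 reversals, and that MP Week 13 should open at Day 85, because SAP 6.5.1 wants subjects switching from placebo to have "had at least 85 days on filgotinib prior to their first semen collection while on filgotinib treatment". The documents do not support this. That rule secures drug exposure, whereas the reversibility definition sets no minimum time off drug. An early reversal is correctly a reversal by Week 13. A Day 85 limit would remove the label from any pre-Amendment 2 first collection with a stop lag over 6 days (91 − 7 = 84). Monitoring ends once reversibility is met, so such a subject may have no later sample.

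**Conclusion.** The point holds in a limited form. The Table 3-5 offsets are exact. Protocol-compliant collections can overrun the upper limits by up to 4 days, or 6 after an invalid first sample, if the 14 days run from the visit. Delays beyond the visit tolerance go further. The result is a label one visit late or, at Week 52, no analysis visit and no place in the by-visit and cumulative table.

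Two stronger readings should be resisted. Compliant late samples are not generally misdated or lost; that needs a late first sample after an already late visit, or a replaced first sample. Nor do the documents say that a reversal after Day 377 is counted as a failure. The SAP leaves its treatment in the overall reversibility column open, and the listing and disposition would show it.

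The chance for any one subject looks small, but the documents do not allow it to be estimated. One subject moves an arm's reversal percentage by 100/n points: 20 for n = 5 and 16.7 for n = 6. Those denominators come from Table 6-3, which is labelled hypothetical, so they show only that one subject can matter when few enter the phase.

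**What to change.** Amend Table 3-5:

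| Visit | Lower limit | Upper limit |
|---|---|---|
| MP Week 13 | 8 | 111 |
| MP Week 26 | 112 | 202 |
| MP Week 39 | 203 | 293 |
| MP Week 52 | 294 | open |

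The upper limits are nominal +20, the allowance Table 3-4 gives Week 13 on treatment (112 − 92). They hold every date in the working (110 ≤ 111, 201 ≤ 202, 292 ≤ 293), and the open end holds Day 383.

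Keep the lower limit at FU Day 8. Show days off drug at the reversing sample, so that reversals before a full 13 weeks off drug can be identified. State one dating rule for the FU day. Reconcile the schedule's starting point in SAP 1.2 with Table 3-5 and Protocol 6.7.

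The cost is one table, one displayed variable and some wording. The SAP introduction already sends later changes to the clinical study report. The one trade-off is that successive pre-Amendment 2 collections stay in successive windows for stop lags up to 70 days (182 − 70 = 112) instead of 77.
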